4.1 Primary Endpoints

Functionality

- the system is able to accurately guide the user to ensure correct initial placement (verified by X-ray)
- the system is able to detect tube movement/displacement during ongoing use (verified by markings on the tube)
- the system automatically stops feeding when tube displacement is detected
- the system automatically stops feeding when reflux is detected
- the system automatically inflates the balloon when a reflux episode is detected

Safety

- occurrence of device related adverse events

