6.2.2 Treatment

Following the screening procedure staff will utilize the smART System to provide enteral feeding to the patient. Feeding tube insertion and commencement of feeding should be done per patients' need and per local hospital procedures.

6.2.3 Study Specific Procedures:

- Videotaping of subject

Following the completion of the informed consent procedure and prior to feeding tube placement, a video recording of the patient will commence. The camera will be placed across from the patient focusing on the facial area and will allow recording of any movement of the tube for later comparison with the data logs recorded by the smART console. All recorded data must be attached to the CRF and serves as an integral part of the analyzable data for the study.

Specific video procedures will be supplied to the site as part of the study MOP binder.

- Initial Tube Placement:

Vital signs should be noted within 10 minutes of feeding tube insertion.

Study staff should follow the device instructions for use and specific instructions provided by the console during initial tube placement. Time of tube placement is recorded by the console.

Once initial placement is confirmed by the system, verification of correct placement should be performed by abdominal X-ray (gold standard). Note: X-ray should be performed as needed and according to hospital procedures. Once placement confirmation is obtained via x-ray, staff should use a permanent marker to indicate the edge of the nostril on the feeding tube (this mark will enable the staff to verify malpositioning warnings if they occur during on-going use).

- **Ongoing Use**

If system alerts of tube displacement during ongoing use, staff should record the event and verify based on the tube marking if malpositioning occurred and document the event. The need for tube reinsertion/repositioning should be evaluated and performed as needed.

When a reflux episode is detected by the system, the following will be initiated:

1. feeding stops
2. feeding tube balloon will automatically be inflated by the system
3. an alert will sound
4. The Y-piece block opens allowing for feeding system decompression initiating free flow of gastric content into the collection bag. The system will automatically record data relevant to reflux episodes and store it.

- **Feeding Information**

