Every smART feeding tube removal should be documented in the CRF and the relevant device information (i.e., serial number) should be recorded. If a smART tube is replaced by a different smART tube, the reason for replacement should be documented and the serial number of the new device being used should be recorded.

- **Endoscopy/esophageal imaging**

One third of the study population will undergo endoscopy to evaluate potential trauma to the esophagus as a result of balloon inflation.

Endoscopy will be indicated for those patients who:

- Have been enrolled in the study for a duration of more than 5 days;

Or,

- Had noticeable blood residue on the feeding tube following tube removal.

PATIENT SAFETY THROUGH TECHNOLOGY

Date issued:
05 Dec2018

SUBJECT: Functionality and Accuracy of the smART System in Real-Life ICU Settings

Number: CLT3_SY_P001

Revision 08

Page 21 of 38

If by the time patient number 13 is enrolled, no endoscopies have been performed, the remaining 7 patients will undergo endoscopy for local evaluation of trauma in the area of the esophagus where the balloon is inflated.

Every effort will be made to obtain at least 7 patients with endoscopic assessment.

Procedure - Following tube removal (within 5 hrs.) patients eligible for endoscopy (based on the above definition) shall undergo an endoscopic procedure to evaluate the balloon inflation site. Specifically, any noticeable trauma to the esophagus shall be recorded in the relevant CRF pages (e.g., adverse event form).

- Aspiration of gastric contents recording

Local site procedure for tracheal suction should be followed as needed and according to hospital procedures. Once every eight hours a sample of at least 2 cc should be instilled in a LUKI trap. The sample should be appropriately labeled and recorded by the medical staff in the bed side CRF log (Pepsin Test). The sample should be kept frozen until transportation to the lab.

- Used/Unused Devices

Used devices will be returned back to the bag in which they were provided in by the sponsor. All the bags will be collected by the sponsor, and accountability logs will be updated accordingly.

All unused devices and study materials will be collected by the sponsor at the end of the study.

- Staff Questionnaires:

At the end of the study, staff will be required to complete a usability questionnaire assessing the ease of use and functionality of the device (refer to Appendix 2).

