6.2.6 Study Schedule

Procedures	Screening/ enrollment	Medical Device Placement	Ongoing use	Termination
Day	1	1	Up to 7	2.3 up to 7
Informed Consent	+			
Eligibility Criteria	+			
Physical Exam	+			
Pregnancy test (if applicable)	+			
Vital Signs		+	+	+
Lab Data				+
Medical Device Administration		+	+	
GRV Measurements			+ as needed and according to procedures	
Aspiration of gastric contents recording			+	
Pepsin Test			+ Collected every 8 hrs. during routine tracheal suction	
Adverse Events	+	+	+	+
Concomitant Medication		+	+	+
Patient positioning		+	+	

SUBJECT: Functionality and Accuracy of the smART System in Real-Life ICU Settings

Number: CLT3_SY_P001

Revision 08

Page 23 of 38

Information regarding nutritional supplement administration		+	+	
Patient responses		+	+	
Endoscopy (performed on up to 7 subjects)			+ if blood residue is visible on balloon following tube removal (within 5hrs. of tube removal)	+ On subjects enrolled for a duration of more than 5 days (within 5hrs. of tube removal)

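### The tube mark, the only reference named for displacement detection, is to be read only after an alert, and the video that could show misses has no stated counting rule

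*Combined protocol and SAP*

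**What the plan says.** One of the primary functionality endpoints in section 4.1, repeated in the synopsis, is that "the system is able to detect tube movement/displacement during ongoing use (verified by markings on the tube". No other reference is named for it.

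Section 6.2.3 gives the mark's purpose under Initial Tube Placement: "this mark will enable the staff to verify malpositioning warnings if they occur during on-going use". The instruction to read it stands in the Ongoing Use part: "If system alerts of tube displacement during ongoing use, staff should record the event and verify based on the tube marking if malpositioning occurred". The schedule in 6.2.6 has no row for mark readings. Section 6.2.15 (tube replacement) asks for a visual inspection of the tube and refers back to 6.2.3, but does not mention the mark.

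Section 6.2.3 also plans a facial video, started before placement, which "will allow recording of any movement of the tube for later comparison with the data logs recorded by the smART console". The recorded data are said to be something that "serves as an integral part of the analyzable data for the study". Details are placed elsewhere: "Specific video procedures will be supplied to the site as part of the study MOP binder". That binder is not among the documents.

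The same section provides for X-rays taken as needed in routine care, with a copy kept in the study forms.

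Section 9.2 describes generic summaries and tests. It contains no detection rate, no count of misses and no analysis of video against logs. Section 9.1 says the study is descriptive and that its purpose is to validate functionality and accuracy.

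**The concern.** A detection claim needs two counts: displacements that occurred, and how many of them the system flagged. If the reference is consulted only when the system flags something, the device selects the events on which it is judged. A displacement that raised no alert prompts no mark reading and leaves no trace in the mark data. A report based on the named reference could then show excellent agreement while saying nothing about misses.

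A miss matters because section 1.2 describes an automatic feeding stop when the tube moves out of position. An undetected displacement loses that trigger. The separate trigger, on gastric content in the esophagus, remains.

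The baseline is a second weakness. Marking is instructed only under Initial Tube Placement. Section 6.2.3 allows the tube to be repositioned, and 6.2.15 lets a patient continue with a new tube. Neither states that a fresh mark is made. Without one, even the check that follows an alert may compare against an outdated position.

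**Working it through.** The plan gives no figure to reproduce for this endpoint. It states 20 subjects without an expected number of displacements, a target rate or a precision. The check is therefore a reading of what each source can show, followed by one illustration.

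**What each source can show**

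- *Tube mark, as instructed:* read after an alert. It separates confirmed from unconfirmed alerts. It holds no observation of a displacement without an alert.
- *Facial video against console logs:* does not depend on alerts, so it could show misses. It is not named in 4.1. The documents define neither the movement that counts, nor how it is matched to an alert, nor how an unmatched movement is counted.
- *Routine X-rays:* might show a displaced tip incidentally. They are taken as needed and are not linked to this endpoint.

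**The two proportions**

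Let TP be displacements with an alert, FP alerts without a displacement, and FN displacements without an alert.

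- Share of alerts confirmed = TP / (TP + FP). The mark data supply both terms.
- Share of displacements detected = TP / (TP + FN). The mark data supply no FN.

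**Illustration (assumed counts, mark data alone)**

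Take TP = 10 and FP = 0. The share of alerts confirmed is 10/10 = 100%, with an exact (Clopper-Pearson) 95% interval of 69.2% to 100%. The same mark data arise with:

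- FN = 0 (10 displacements): 10/10 = 100% detected
- FN = 10 (20 displacements): 10/20 = 50% detected
- FN = 30 (40 displacements): 10/40 = 25% detected

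The mark data cannot separate these cases. That conclusion follows from when the mark is read and does not depend on the counts chosen.

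**Burden of reading the mark regardless of alerts**

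An 8-hourly contact already exists. The schedule lists the pepsin sample as "Collected every 8 hrs. during routine tracheal suction", and 6.2.3 says "Once every eight hours a sample of at least 2 cc should be instilled in a LUKI trap". Participation of 56 to 168 hours gives 56/8 = 7 to 168/8 = 21 contacts per patient, or 140 to 420 over 20 patients.

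**The case against.** The strongest reply is that the video already closes the gap. It starts before placement, is meant to capture tube movement whether or not an alert sounds, and is declared analyzable. Much of this stands. A reader might infer that the study cannot observe missed displacements at all; the documents do not support that. What remains is narrower: the endpoint does not name the video, and the analysis section does not say how a miss is defined or counted. The binder may hold part of this, so the fair statement is that the protocol does not state it. A rule for a primary endpoint nevertheless belongs in 4.1 and 9.2, where it is fixed before the logs are seen.

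Staff may also look at the mark without an alert. Nothing forbids it, but nothing asks for it, so such readings would be unsystematic.

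A reader might infer that a missed displacement means feeding continues unchecked. Section 1.2 gives a second trigger for the stop, so that goes too far.

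On re-marking, a replacement tube can reasonably be read as a new initial placement, and the device instructions for use, which are not provided, may cover it. The gap is clearer for repositioning than for replacement.

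Finally, this is a 20-patient descriptive study, and an elaborate matching scheme would be out of proportion. That stands and limits the remedy. It does not remove the need for a denominator that is independent of the device's own alerts.

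**Conclusion.** The concern holds in limited form. As instructed, the only reference named for displacement detection yields the proportion of alerts confirmed, not the proportion of displacements detected. The video could supply the missing count and X-rays might do so incidentally, but neither is named as a reference in 4.1 or given a counting rule in 9.2. A new baseline mark is not stated after repositioning, nor explicitly after replacement.

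The size cannot be estimated, because the documents give no event counts. The range of 25% to 100% detection behind 10 of 10 confirmed alerts is illustrative and describes the mark data alone, not the full planned data set.

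This should be fixed before the first patient, because mark readings and baseline marks not made at the bedside cannot be recreated. It does not invalidate the study, since the video keeps misses recoverable in principle. Confidence is medium because the binder and the device instructions could not be seen.

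**What to change.** 1. In 6.2.3, have bedside staff log the mark's position relative to the nostril, alert or not, at each existing 8-hourly tracheal sample and before staff move the tube. Make a new baseline mark after each repositioning or replacement.
2. In 4.1 and 9.2, name these readings and the planned video-versus-log comparison as the reference for missed displacements. Before the first patient, fix the smallest external shift that counts in the analysis and how a shift is matched in time to an alert.
3. Report two proportions separately: reference-detected external displacements that had a matching alert, and alerts confirmed. Use intervals that allow for several events in one patient. State that the mark and the facial video show external movement, whereas the sensors report tip location, so the result is not sensitivity to tip migration.

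The cost is about 7 to 21 log lines per patient, one more each time the tube is moved, and wording in three sections. Filming and some comparison with the logs are already planned, but matching individual events adds work. If filming spans the whole of participation (an assumption), the footage is 20 × 56 = 1,120 to 20 × 168 = 3,360 hours. The resulting detection figure may be less favourable than the share of alerts confirmed.

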Insertion of nasal feeding tubes can be performed blindly at bedside or with fluoroscopic or endoscopic guidance into the stomach.

SUBJECT: Functionality and Accuracy of the smART System in Real-Life ICU Settings

Number: CLT3_SY_P001

Revision 08

Page 9 of 38

[figure not shown]
Although generally safe and effective, they are usually inserted blindly at the bedside and there is a wide spectrum of known complications associated with feeding tube placement. The most common serious complication is misplacement of the feeding tube into the bronchial tree with resulting pneumonitis, pneumonia, and/or pneumothorax if not recognized. This is reported to occur in **2.4%–3.2% of nasogastric insertions** (James L, et al. 2012).

Recent studies have suggested that 0.1 to 0.3% of all patients who were blindly placed of their feeding tubes die as a result of bronchopulmonary injury from misplaced tubes (Sorokin R et al. 2006) (Aguilar-Nascimento JE, et al. 2007).

It is estimated that approximately **1.2 million feeding tubes are placed each year in the United States alone** (Koopmann MC et al. 2011). If these tubes were placed blindly this would translate to **3,600 to 8,400 pulmonary injuries, and 1,200 to 3,600 deaths in the United States each year**. Hundreds of thousands of patients require NG tubes each year in the UK. Although the precise number is not known, the NHS Purchasing and Supply Agency (PASA) which distributes NG tubes has estimated that between 750,000 to 1,000,000 tubes are used each year within the NHS1. In addition to those used within the NHS, private hospitals, hospices and nursing homes are expected to greatly increase the number of tubes used annually. Currently, X-ray is the gold standard method for detecting the position of nasogastric tubes (Hedberg et al, 2005). However, staff does not use it routinely due to cost, risk of radiation exposure, and delay in feeding (National Patient Safety Agency, 2011; 2005). In addition, the National Patient Safety Agency (NPSA) has drawn attention in 2011 to the risk of misinterpretation of X-rays used to confirm the position of a nasogastric tube. Positioning complications are also occurring throughout the duration of the use of the tube. Movement of the distal tip of the feeding tube occurs even when the NG tube is taped in place. This is most likely to occur with soft, small-bore NG tubes. Malpositioning of the indwelling tube may result in injury or aspiration.

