Patient information will be recorded from hospital source at the end of the study for each patient. The information will include feeding times, food amounts and types, medications provided, patient positioning, GRV times and amounts.

- **Gastric Residual Volume (GRV)**

Local site procedure for GRV should be followed as needed and according to hospital procedures. Every occurrence of GRV is supposed to be recorded by the medical staff in hospital sources (according to hospital standards).

- **Patient Positioning**

Every occurrence of patient re-positioning is supposed to be recorded by the medical staff in hospital sources. This information will later be correlated to the occurrence of reflux as recorded by the system.

SUBJECT: Functionality and Accuracy of the smART System in Real-Life ICU Settings

Number: CLT3_SY_P001

Revision 08

Page 20 of 38

- **X-Ray imaging**

Local site procedure for X-ray should be followed as needed and according to hospital procedures. Each time a thorax x-ray image is taken (as part of the patient care). Once feeding tube initial positioning is performed, X-Ray should be taken as part of the usual gold-standard care. A copy of the X-ray should be documented as part of the study CRFs/Forms.

- **Patient general clinical information**

In addition to the CRF's, patient clinical information will be collected directly from the hospital's electronic medical record by the hospital's IT department and provided to the sponsor. The clinical information may include a summary and daily reports and diagnosis, vital signs, imaging data, medications and laboratory reports, breathing and respiratory support parameters, physicians and nurses' notes and medical orders, etc.

The collected information will include valid data from 48 hours prior to feeding tube insertion up until 24 hours after the end of the study.

This information will allow for the analysis of the secondary endpoint dealing with the correlation between patient clinical information and the occurrence of reflux and sensors data.

The data may be collected at various time intervals during the study or at the end of the study once all patients have completed the study.

- **Removal of feeding tube**

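### The routine thorax-film instruction in 6.2.3 is unfinished, so ongoing tube displacement is checked only from outside the body, by nostril mark and facial video, which may miss movement of the tip

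*Combined protocol and SAP*

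**What the plan says.** **Endpoint.** Section 4.1 lists as a primary functionality endpoint that "the system is able to detect tube movement/displacement during ongoing use (verified by markings on the tube").

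**The mark.** In 6.2.3 (Initial Tube Placement), "verification of correct placement should be performed by abdominal X-ray (gold standard"). Once the film confirms placement, "staff should use a permanent marker to indicate the edge of the nostril on the feeding tube". Under Ongoing Use, staff are told to check the mark when the system alerts to displacement. No check is scheduled in the absence of an alert.

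**The video.** Section 6.2.3 also requires a video of the patient's face, started before tube placement, to capture tube movement for later comparison with the console logs. It counts as part of the data to be analysed.

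**Later films.** Under X-Ray imaging in 6.2.3 stands the fragment "Each time a thorax x-ray image is taken (as part of the patient care"). It has no main clause. The text then turns to the film after initial positioning and adds: "A copy of the X-ray should be documented as part of the study CRFs/Forms". For the record extract, 6.2.3 says: "The clinical information may include a summary and daily reports and diagnosis, vital signs, imaging data, medications and laboratory reports". Its purpose is given as: "This information will allow for the analysis of the secondary endpoint dealing with the correlation between patient clinical information" and the occurrence of reflux and sensor data.

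**Background.** Section 1.1 states: "Movement of the distal tip of the feeding tube occurs even when the NG tube is taped in place". It adds that this is most likely with soft, small-bore tubes, and it calls X-ray the gold standard for the position of nasogastric tubes.

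**The concern.** The device is described in 1.1 and 1.2 as locating the tube tip relative to the lower esophageal sphincter. The references named for ongoing displacement see only the part of the tube outside the body. If the tip moves while the external length changes little or not at all, two errors are possible. A correct alert could be recorded as unconfirmed because the mark has not moved. A displacement with no alert could go unseen, because nothing prompts a check of the mark and the video cannot show the tip.

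The second error matters more. Section 1.1 links malposition of an indwelling tube to injury or aspiration, and the study is meant to validate accuracy. Films taken for routine care could show the tip whether or not the system has alerted, and the protocol comes close to asking for them without doing so.

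**Working it through.** The plan gives no figure on this point, so there is nothing to reproduce. The check is mainly a comparison of the sources that could verify tube position during ongoing use.

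| Source | When it is available | Can it show the tip? | Role stated in the plan |
|---|---|---|---|
| Nostril mark (4.1, 6.2.3) | Checked after a displacement alert | No | Verifies the primary endpoint |
| Facial video (6.2.3) | Not tied to alerts | No | Compared with console logs |
| Initial abdominal film (6.2.3) | Once, at placement | Yes | Verifies initial placement |
| Later routine thorax films (6.2.3) | Not tied to alerts | Sometimes | None stated for tube position |

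1. **Is a role for later films stated elsewhere?** The study schedule (6.2.6) has no X-ray row. The endpoints (4.1, 4.2) mention X-ray only for initial placement. Section 9.2 does not mention films. The copy for the CRF is of a single X-ray and follows the sentence on initial positioning, so it is unclear whether it covers later films. The record extract may contain imaging data, but its stated purpose is a secondary correlation.

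2. **What can be estimated?** Checks of the mark follow alerts, so the mark yields confirmed and unconfirmed alerts, which is a positive-predictive-value type of figure. The video adds information on external movement without an alert. Neither gives sensitivity or negative predictive value for tip position. PPV and NPV appear in the list of abbreviations, but 9.2 defines neither.

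3. **How many films might there be?** The documents give no frequency. Assume one film every 1 to 3 days. Section 5.3 gives 2.3 to 7 days per patient, and 9.1 gives 20 subjects. Films per patient = days on study / days between films.

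| Days on study | Film interval | Films per patient | In 20 patients |
|---|---|---|---|
| 2.3 | 3 days | 2.3 / 3 = 0.77 | 0.77 x 20 = about 15 |
| 2.3 | 1 day | 2.3 / 1 = 2.3 | 2.3 x 20 = 46 |
| 7 | 3 days | 7 / 3 = 2.33 | 2.33 x 20 = about 47 |
| 7 | 1 day | 7 / 1 = 7 | 7 x 20 = 140 |

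The range is about 0.8 to 7 films per patient, roughly 15 to 140 in all. At the low end some patients would have none. These counts include films that turn out not to show the tip.

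**The case against.** **The video is a second check.** A reader might infer that displacement is judged by the nostril mark alone and that a missed displacement could never be seen. The documents do not support that: the video runs independently of alerts and is compared with the console logs. What remains is that it, too, sees only the external tube.

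**Section 1.1 does not say the mark stays still.** It says the tip moves while the tube is taped. That the external length is unchanged is an inference, and no rate is given. Section 9.2 also has no rule that would score an unconfirmed alert as false. So the external references may miss tip movement; the documents do not establish that the endpoint will be misclassified.

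**The fragment may be a punctuation slip.** Joined to the sentence before it, it could mean that local X-ray procedure applies whenever a thorax film is taken. On that reading no study instruction was lost. Later films still have no stated role in verifying position.

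**The films are not simply unused.** Copies may be meant for the CRF, and imaging data may enter the secondary correlation. The accurate statement is that no role in verifying tube position is given.

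**Thorax and abdominal films.** A reader might take these as a contradiction. They are not: one is the routine-care film, the other the film at initial placement.

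**The yield may be small.** Films are snapshots, and repositioning is considered after each alert, so few films may coincide with a displacement. This stands. It limits what the added table can show about sensitivity.

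**Conclusion.** The point holds as a gap that is cheap to close, not as a fault that invalidates the study. The thorax-film sentence is incomplete, and no section gives later films a role in verifying position. Both planned checks of ongoing displacement are external, so tip displacement without an alert has no tip-level reference, and an alert for tip movement alone could be recorded as unconfirmed.

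This rests on two things the documents do not settle: how often the tip moves without visible change at the nostril, and how often films are taken. The first is inferred from 1.1. The second is assumed, at one film every 1 to 3 days, which gives roughly 15 to 140 films before non-evaluable ones are excluded. The gap itself depends on neither number. The analysis is descriptive, so no error rate or power claim is affected.

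**What to change.** 1. **Complete the sentence in 6.2.3.** For each routine film taken while the tube is in use, with or without an alert, record the film time, the tube or tip position stated in the existing clinical reading (or not visible), and the console status at that time. Position should preferably be abstracted before the console status is looked up.
2. **Make imaging data a required part of the record extract**, in place of an optional one, and state whether the CRF copy covers later films.
3. **Add a descriptive table to 9.2** of console status (in position, displacement alert) against film position (in place, displaced, not visible), shown beside the mark and video results. Give the number of patients as well as films, and account for repeated films per patient in any interval.

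The cost is abstraction time. No extra film, reader or procedure is needed. Some thorax films will not show the tip and will count as not evaluable, and few displacements may be captured. The table should then be reported as limited evidence on missed displacement.

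### Seven endoscopies is a minimum to aim for in 6.2.3 but a maximum in the 6.2.6 schedule, so an eighth indicated patient gets conflicting instructions

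*Combined protocol and SAP*

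**What the plan says.** The endoscopy item in protocol section 6.2.3 (Study Specific Procedures) contains five statements that bear on the number of endoscopies.

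- Scale: "One third of the study population will undergo endoscopy to evaluate potential trauma".
- Indication: "Endoscopy will be indicated for those patients who" meet either of two conditions. The first is "Have been enrolled in the study for a duration of more than 5 days"; the second is visible blood on the tube once it has been taken out.
- Force: "patients eligible for endoscopy (based on the above definition) shall undergo an endoscopic procedure", within 5 hours of tube removal. No numerical limit is attached.
- Fallback: "If by the time patient number 13 is enrolled, no endoscopies have been performed, the remaining 7 patients will undergo endoscopy".
- Aim: "Every effort will be made to obtain at least 7 patients with endoscopic assessment".

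The table in section 6.2.6 (Study Schedule) labels the row "Endoscopy (performed on up to 7 subjects"). It lists the same two routes, except that the blood must be seen on the balloon, whereas 6.2.3 refers to the feeding tube.

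Section 5.3 lets a patient take part for 56 hours up to 7 days. The reasons for ending participation in 6.2.7 are the 7-day maximum, transfer, withdrawn consent, a related adverse event and death. Section 6.2.14 adds withdrawal by the investigator and failed insertion.

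**The concern.** The two sections bound the same count in opposite directions, and neither says which prevails. Up to seven indicated patients, a site can follow both. At the eighth, 6.2.3 requires the endoscopy and the schedule puts it outside the stated number.

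Endoscopy is the only scheduled direct look at the esophagus where the balloon inflates, and 6.2.3 says that it is done to look for trauma from that inflation. If the schedule is taken as a limit, places are used up as tubes come out. Seven patients who qualified only by staying past day 5 could exhaust them. A later patient with blood on the tube, which is the protocol's own warning sign, could then go unscoped. The site and the IRB also need one consistent statement of how many ventilated patients may have this invasive procedure.

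**Working it through.** **1. Where the figure 7 comes from.** The sample size is 20 (section 9.1). One third of 20 is 6.67, which rounds up to 7. The patients remaining after number 13 are 20 − 13 = 7. Both routes give the plan's figure, so the number is consistent; the conflict is over the direction of the bound.

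**2. The instructions side by side.**

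| Patients meeting a 6.2.3 condition | 6.2.3 requires | 6.2.6 allows | Compatible? |
|---|---|---|---|
| 7 or fewer | all of them | all of them | yes |
| 8 or more | all of them | 7 | no |

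**3. Can an eighth arise?** Yes. Nothing in 6.2.7 routinely ends participation between day 5 and day 7, and passing day 5 is enough without any blood. The number indicated can in principle be anything from 0 to 20.

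**4. How likely is it?** The documents give no indication rate. Assume that each of the 20 patients meets a condition independently with probability p, and that none refuses. With X ~ Binomial(20, p), the conflict occurs with probability P(X ≥ 8). When it occurs, the mean number of indicated patients beyond the limit is E[max(X − 7, 0)] / P(X ≥ 8).

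| Assumed p | P(more than 7 indicated) | Mean number beyond 7, when it happens |
|---|---|---|
| 20% | 3.2% | 1.41 |
| 30% | 22.8% | 1.81 |
| one third | 33.9% | 2.00 |
| 40% | 58.4% | 2.48 |
| 50% | 86.8% | 3.55 |

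**5. Placing p.** Assume further that all 20 patients pass 56 hours and then leave at a constant daily rate h. The chance of passing day 5 is (1 − h)^(5 − 56/24) = (1 − h)^2.67.

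| Assumed h | p from the 5-day condition alone | P(more than 7 indicated) |
|---|---|---|
| 20% a day | 55.2% | 94.4% |
| 30% a day | 38.6% | 53.4% |
| 40% a day | 25.6% | 11.4% |
| 50% a day | 15.7% | 0.8% |

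The result runs from about 1% to 94% over plausible leaving rates. The tables show that an eighth indicated patient is a practical possibility; they do not estimate how often it will happen.

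**The case against.** **The schedule entry is only a bracketed note in a table.** It does not expressly forbid an eighth endoscopy, the operative instruction is in 6.2.3, and a site might read the note as an estimate. That reading is possible, but the text does not state it, and a stated upper number is naturally read as a limit. The conflict stands.

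**The probabilities rest on an assumed p.** This is correct, and they should carry little weight. The contradiction is in the wording and needs none of them.

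**Three stronger readings are tempting, and the documents do not support them.**

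- A reader might infer that the plan promises endoscopy in one third of patients and will fail to deliver it, since the forced top-up fires only if none has been done by patient 13. The same subsection, however, presents 7 as something every effort will be made to reach. The chance of reaching it depends on how that effort works. At p = 20% it is 14% if the effort adds no one and 61% if it brings in half of the non-indicated patients among numbers 14 to 20. It is 100% if it brings in all of them: one or more done by patient 13 plus seven makes at least eight, and none done triggers the fallback, which gives seven. That range settles nothing.
- A reader might infer that the limit would fill in order of enrolment. The documents do not say so. Endoscopy follows tube removal, the schedule lists the blood trigger under ongoing use, and stays can overlap. Order of removal is the better description.
- A reader might infer that the wider blood trigger is the right one. Section 7.1.2 anticipates nasal bleeding during insertion, so blood on the tube need not come from the esophagus. Which trigger to use is the sponsor's choice.

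The patient-13 fallback does not appear in the schedule, but its absence from a summary table is not an error.

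**Conclusion.** The inconsistency is real and is in the current text: seven is a minimum to aim for in 6.2.3 and a maximum in 6.2.6, and an eighth indicated patient cannot be handled in line with both. Under an assumed indication rate of 20% to 50% per patient, with independence and no refusals, this would arise in 3% to 87% of trials and affect on average 1.4 to 3.6 patients when it did.

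It is minor. Adverse events are recorded in all patients (7.3), the analysis is descriptive (9.1), and no endpoint or test depends on reaching 7. A reader should not conclude that the primary safety endpoint or the sample size of 20 is undermined. What is at stake is narrower: whether a patient who meets the protocol's own indication might miss the examination because of a count in a table.

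**What to change.** In 6.2.6, replace the bracketed limit in the endoscopy row with: *performed on all subjects indicated under 6.2.3; target at least 7*.

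In the same amendment, the sponsor should choose one blood trigger, feeding tube or balloon, and use it in both sections. Rewording the one-third sentence in 6.2.3 as a target is optional editing.

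The cost is a short wording amendment. The downside is that the total may exceed 7, but only through endoscopies that 6.2.3 already requires. Measured against a strictly applied limit, and under the same assumptions, the mean number of extra endoscopies per trial is the product of the last two columns of the table in step 4. That is 0.032 × 1.41 ≈ 0.05 at p = 20%, 0.228 × 1.81 ≈ 0.4 at 30%, 0.584 × 2.48 ≈ 1.4 at 40% and 0.868 × 3.55 ≈ 3.1 at 50%.
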